### 6.9 **Ophthalmic Examinations**

Ophthalmic examinations of both eyes will be performed at the screening and baseline visits and at each visit after study agent administration, including each long-term follow-up visit. These examinations will include slit lamp examination, tonometry, indirect ophthalmoscopy and retinal biomicroscopy. Signs of inflammatory responses will be quantified using a standard 0 to 4+ cells and flare grading system [59]. On the visit at which the study agent is administered, IOP in the study eye will be measured about 30 minutes after study agent administration is completed.

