#### 7.2.1.2 Intensity of an Adverse Event

All AEs will be assessed by the investigator using the following guidelines to quantify intensity:

- Mild: Events that do not interfere with daily activities and require no medical intervention.
- Moderate: Events that cause some interference with daily activities and may require simple medical interventions.
- Severe: Events that prevent usual daily activities and require medical intervention.
- Life-threatening: Any adverse drug experience that places the subject, in the view of the investigator, at immediate risk of death from the reaction as it occurred, i.e., it does not include a reaction that had it occurred in a more severe form, might have caused death.
- Fatal: Any AE that causes the death of the subject. Except for sudden and unexpected death, death is not an AE, but rather the event that caused the subject to die is the AE.

Changes in the intensity of an AE should be documented to allow an assessment of the duration of the event at each level of intensity to be performed. AEs characterized as intermittent require documentation of onset and duration of each episode.

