# 7.3 Reporting Procedures

#### 7.3.1 Adverse Events

All AEs should be captured on the appropriate electronic case report form (eCRF). Information to be collected includes event description, date of onset, intensity, relationship to study agent, relationship to the intravitreal injection procedure used to administer the study agent, action taken, date of resolution or stabilization of the event, seriousness, and outcome (resolved, ongoing or death caused by the AE). All AEs occurring while on study must be documented and treated appropriately regardless of relationship. All AEs will be followed until resolution, until the condition stabilizes, until the event is otherwise explained, or the subject is lost to follow-up.

Any medical condition that is present at the time that the subject is screened should be considered as a pre-existing condition and not reported as an AE; however, if it deteriorates at any time during the study it should be recorded as an AE.

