4.1 General Study Design

This is a non-randomized, open-label, Phase 1/2 dose escalation study of the safety and efficacy of rAAV2tYF-CB-hRS1 administered by intravitreal injection in one eye in individuals with XLRS. The primary objective is to evaluate safety and the secondary objective is to evaluate efficacy.

Each participant is to receive rAAV2tYF-CB-hRS1 by intravitreal injection in one eye on a single occasion as outlined in the schematic below.

		Number of Dose Level				
Group ^a	Age (yr)	Subjects	vg/mL	Volume	vg per eye	
1A	≥ 18	3	1.43 × 10 ¹²	0.07 mL	1 × 10 ¹¹	
1B	≥ 18	3	1.43 × 10 ¹²	0.07 mL	1 × 10 ¹¹	
2	≥ 18	3	4.3 × 10 ¹²	0.07 mL	3 × 10 ¹¹	
2A	6-17	Up to 6	4.3 × 10 ¹²	0.07 mL	3 × 10 ¹¹	
3	≥ 18	3	4.3 × 10 ¹²	0.14 mL	6 × 10 ¹¹	
4	≥ 6	Up to 15	MTD ^b	MTD	MTD	

Schematic of Study Design:

^a Visual acuity not better than 58 Early Treatment Diabetic Retinopathy Study (ETDRS) letter score in Group 1A, 63 in Groups 1B, 2, 2A & 3, 68 in Group 4.

^b MTD = maximum tolerated dose determined in Groups 1A, 1B, 2 and 3 for adults, in Groups 1A, 1B, 2, and 3 (adult participants only) and 2A (pediatric participants only) for pediatric participants.

Participants in Groups 1A, 1B, 2 and 3 are at least 18 years of age and receive the vector at a lower dose (Groups 1A and 1B), middle dose (Group 2) or higher dose (Group 3). Participants in Group 1A have visual acuity that is worse than participants in subsequent groups (ETDRS letter score of 58 in Group 1A and 68 in other groups). Participants in Group 2A will be 6-17 years of age and receive the

vector at the middle dose level. Participants in Group 4 will be at least 6 years of age and will receive the vector at the maximum tolerated dose (MTD) determined in Groups 1A, 1B, 2, and 3 for adults; in Groups 1A, 1B, 2, and 3 (adult participants only) and 2A (pediatric participants only) for pediatric participants.

Participants in all groups are selected from individuals who are not being treated with a carbonic anhydrase inhibitor during the study and have not been treated with any carbonic anhydrase inhibitor within the 3 months prior to enrollment in the study. Participants are asked not to begin treatment with a carbonic anhydrase inhibitor within 6 months after study agent administration.

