9.4 Data Analysis Conventions

All data analysis outlined in this SAP will be performed by Statistics & Data Corporation (SDC). Statistical programming and analyses will be performed using SAS[®] Version 9.4 or higher. Output will be provided in Rich Text Format (RTF) for tables and figures and Portable Document Format (PDF) for tables and listings using landscape orientation. All study data for treated subjects will be listed by group, subject, and visit (as applicable) unless otherwise specified. Only a disposition listing will be created for screen failed subjects.

Summaries for continuous and ordinal variables will include the number of observations (n), arithmetic mean, standard deviation (SD), median, minimum, and maximum. Minima and maxima will be reported with the same precision as the raw values; means and medians will be presented to one additional decimal place than reported in the raw values. Standard deviations will be presented to two additional decimal places than reported in the raw values. Summaries for discrete variables will include frequency counts and percentages. All percentages will be rounded to one decimal place (i.e., XX.X%). Change from baseline will be calculated as follow-up visit values minus the baseline value.

All statistical tests will be two-sided with alpha level of 0.05. Unless otherwise specified, summaries will be presented by group (1A, 1B, 2, 2A, 2+2A, 3, 4, 3+4, and all subjects) and, where appropriate, visit.

Unscheduled visits will not be summarized. Study visits will be referred to in all tables and listings with the expected study day/month/year corresponding to the visit to enable reviewers to understand the assessment timing without referring to the protocol visit schedule. The following table shows the scheduled study visits, their planned study day:

Scheduled Visit	Planned Study Day
Visit 1	Screening
Visit 2	Baseline
Visit 3	Day 0
Visit 4	Day 1
Visit 5	Day 7
Visit 6	Day 14
Visit 7	Month 1
Visit 8	Month 2
Visit 9	Month 3
Visit 10	Month 6
Visit 11	Month 9
Visit 12	Month 12
Visit 13	Year 2
Visit 14	Year 3
Visit 15	Year 4
Visit 16	Year 5
1	

10. Disposition of Subjects

The following disposition items will be summarized:

- The number of subjects screened (who signed the informed consent/assent form)
- The number of screen failures
- The number of subjects enrolled (who met the enrollment criteria)
- The number of subjects treated (who received an intravitreal injection of study agent)

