Additional summaries of TEAEs will be provided showing the number and percentage of subjects who experienced at least one TEAE. These summaries will be presented by SOC and PT using MedDRA Version 20.0. Non-ocular TEAEs will be summarized by group at the subject level by SOC and PT. Ocular TEAEs will be similarly summarized at the subject level for study and fellow eyes separately. If a subject reports the same PT multiple times within the same SOC, that PT will only be reported once within that SOC. As with the PT, if a subject reports multiple conditions within the same SOC, that SOC will only be reported once. In the summary, SOC will be listed in order of descending frequency for all subjects; PTs will be listed in order of descending frequency for all subjects within each SOC.

Separate summaries will be provided for the following categories of AEs:

- Ocular TEAEs (study eye, fellow eyes, both eyes)
- Non-ocular TEAEs
- Grade 3 or 4 local (ocular) or systemic AEs that occur during the 12 months after study agent administration
- Ocular TEAEs related to study agent
- Non-ocular TEAEs related to study agent
- Ocular TEAEs related to intravitreal injection procedure
- Non-ocular TEAEs related to intravitreal injection procedure
- Serious TEAEs
- Serious TEAEs related to study agent
- Serious TEAEs related to intravitreal injection procedure

All AEs will be assessed by the investigator using the following guidelines to quantify intensity:

- Mild: Events that do not interfere with daily activities and require no medical intervention.
- Moderate: Events that cause some interference with daily activities and may require simple medical interventions.

08 August 2017

- Severe: Events that prevent usual daily activities and require medical intervention.
- Life-threatening: Any adverse drug experience that places the subject, in the view of the investigator, at immediate risk of death from the reaction as it occurred, i.e., it does not include a reaction that had it occurred in a more severe form, might have caused death.
- Fatal: Any AE that causes the death of the subject. Except for sudden and unexpected death, death is not an AE, but rather the event that caused the subject to die is the AE.

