Table 14.2.1.2	Best Corrected Visual Acuity – Inferential Statistics
Table 14.2.1.3	Best Corrected Visual Acuity Letter Score - Categorical Summary
Table 14.2.2.1	Spectral Domain Optical Coherence Tomography
Table 14.2.2.2	Spectral Domain Optical Coherence Tomography – Inferential Statistics
Table 14.2.3.1.1	Static Perimetry
Table 14.2.3.1.2	Static Perimetry – Inferential Statistics
Table 14.2.3.2.1	Kinetic Perimetry
Table 14.2.3.2.2	Kinetic Perimetry – Inferential Statistics
Table 14.2.4.1	Microperimetry
Table 14.2.4.2	Microperimetry – Inferential Statistics
Table 14.2.5.1	Reading Speed
Table 14.2.5.2	Reading Speed – Inferential Statistics
Table 14.2.6.1	Contrast Sensitivity
Table 14.2.6.2	Contrast Sensitivity – Inferential Statistics
Table 14.2.7.1.1	Full-field Electroretinography
Table 14.2.7.1.2	Full-field Electroretinography – Inferential Statistics
Table 14.2.7.2.1	Multi-focal Electroretinography

Table 14.2.7.2.2	Multi-focal Electroretinography – Inferential Statistics
Table 14.2.8.1	25-Question Visual Function Questionnaire (VFQ-25)
Table 14.2.8.2	25-Question Visual Function Questionnaire (VFQ-25) – Inferential Statistics
Table 14.2.8.3	Functional Vision Questionnaire for Children and Young People (FVQ_CYP)
Table 14.2.8.4	Functional Vision Questionnaire for Children and Young People (FVQ_CYP) – Inferential Statistics
Table 14.2.9	Fundus Photography
Table 14.3.1	Overall Summary of Treatment-Emergent Adverse Events
Table 14.3.2	Ocular Treatment-Emergent Adverse Events by System Organ Class and Preferred Term
Table 14.3.3	Non-Ocular Treatment-Emergent Adverse Events by System Organ Class and Preferred Term
Table 14.3.4	Grade 3 or 4 Treatment-Emergent Adverse Events that Occurred During the 12 Months after Study Drug Administration by System Organ Class and preferred Term
Table 14.3.5	Ocular Treatment-Emergent Adverse Events Related to Study Agent by System Organ Class and Preferred Term
Table 14.3.6	Non-Ocular Treatment-Emergent Adverse Events Related to Study Agent by System Organ Class and Preferred Term
Table 14.3.7	Ocular Treatment-Emergent Adverse Events Related to Injection by System Organ Class and Preferred Term
Table 14.3.8	Non-Ocular Treatment-Emergent Adverse Events Related to Injection by System Organ Class and Preferred Term
Table 14.3.9	Serious Adverse Events by System Organ Class and Preferred Term

Table 14.3.10	Serious Adverse Events Related to Study Agent by System Organ Class and Preferred Term

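### The planned adverse event tables give no once-per-participant count of intraocular inflammation and nothing on its onset, duration or recurrence

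*SAP*

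**What the plan says.** **Adverse event tables.** SAP 14.1 introduces its breakdowns with "Separate summaries will be provided for the following categories of AEs". The ten categories are built from ocular or non-ocular site, Grade 3 or 4, relationship to agent, relationship to procedure, and seriousness. The matching tables in SAP section 22 follow one pattern, for example "Ocular Treatment-Emergent Adverse Events by System Organ Class and Preferred Term"; two add maximum intensity. A participant is counted once per PT and once per SOC, and ocular events are shown for study and fellow eyes separately.

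**Columns and visits.** SAP 9.4 sets the columns: "summaries will be presented by group (1A, 1B, 2, 2A, 2+2A, 3, 4, 3+4, and all subjects". It adds: "Unscheduled visits will not be summarized".

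**Other outputs that touch inflammation.** SAP 14.5 and 14.7 tabulate shifts from baseline to the worst value in slit-lamp and ophthalmoscopy findings. SAP 15.9 has a fundus photograph item on increased inflammation, read at baseline and Month 12. All adverse events are also listed by subject.

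**What is collected.** Protocol 6.9: "Signs of inflammatory responses will be quantified using a standard 0 to 4+ cells and flare grading system". Protocol 7.2.1.2: "AEs characterized as intermittent require documentation of onset and duration of each episode". Protocol 7.3.1 also records onset, intensity, both relationships, and "date of resolution or stabilization of the event, seriousness, and outcome (resolved, ongoing or death caused by the AE".

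**Why inflammation stands out.** Protocol sections 3 and 5.6 give ocular inflammation in the first 12 subjects, and a possible greater tendency to it in children, as the reason for treating children at the middle dose (Group 2A) before Group 4. Protocol 5.7 says prophylactic steroids may be given to lower the risk of intraocular inflammation.

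**The concern.** Safety is the primary objective, and inflammation is the harm that shaped the design. A reader of the final report will ask how many participants had it, at what dose, when it began, how long it lasted and whether it came back. The data to answer are collected, but no planned table does so. Inflammation coded to several terms appears as several rows that cannot simply be added. The SOC row counts each person once but takes in every other event in that class. Someone will have to count from the listings, and choose which terms belong and what makes an episode with open-label results already in view.

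**Working it through.** **1. The plan's own figures.** The plan gives none for inflammation. Its only numerical safety statement is the exact two-sided 95% limit for dose-limiting toxicity with no events: 1 − 0.025^(1/9) = 33.63% and 1 − 0.025^(1/27) = 12.77%. Both reproduce, and nothing below depends on them.

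**2. What each planned output can answer.**

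| Question | AE tables 14.3.1–14.3.13 | Slit-lamp and ophthalmoscopy shifts | Fundus photographs | Listings |
|---|---|---|---|---|
| Number affected, each counted once | Bounded only (step 3) | By structure, not across structures | Only what is visible at Month 12 | By hand, no fixed definition |
| Days to first onset | No | No | No | By hand |
| Duration | No | No | No | By hand |
| Recurrence | No | No | No | By hand |

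The 0 to 4+ cells and flare grade of Protocol 6.9 is not named in the SAP.

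**3. What the PT rows say about the number affected.** Within one column and one eye, let r₁, r₂, … be the inflammation PT rows. Let S be the SOC row, O the sum of the other PT rows in that SOC, and U the number with any inflammation. If the inflammation terms share the SOC:

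- U ≥ max(r), and also U ≥ S − O
- U ≤ min(Σr, S)

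If the terms fall in different SOCs, the S terms drop out and U ≤ min(Σr, n).

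Take the 2+2A column, with n = 3 + 6 = 9 if Group 2A is full. The rows below are assumptions, since neither document gives the split:

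- One row of 9: U = 9. Nothing is lost on incidence.
- Rows 3, 3, 3 and S = 3: U ≥ 3 and U ≤ min(9, 3) = 3, so U = 3 exactly.
- Rows 3, 3, 3, S = 9 and O = 6: U ≥ max(3, 9 − 6) = 3 and U ≤ min(9, 9) = 9, so U is anywhere from 3 to 9.

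The loss on incidence therefore runs from none to substantial, depending on coding and on how many other eye events share the SOC. The loss on timing is the same in all three cases.

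**4. Dose.** Groups 1A, 1B, 2, 2A and 3 each receive one dose, so their once-per-participant counts add exactly, and 2+2A already pools by dose (3 × 10¹¹ vg). Group 4 is different. SAP 4.1 says "Participants in Group 4 will be at least 6 years of age and will receive the vector at the maximum tolerated dose (MTD", and sets that dose from Groups 1A, 1B, 2 and 3 for adults but also from Group 2A for children. If the two MTDs differ, the Group 4 and 3+4 columns hold more than one dose. Neither document states the MTDs.

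**5. Unscheduled visits.** Protocol 5.4 tells participants to contact the investigator at once for eye pain, redness, photophobia or reduced vision, so a flare may well be examined between scheduled visits. An adverse event found then still enters the adverse event tables. Under SAP 9.4, however, the examination grade would not be summarized. SAP 14.5 and 14.7 speak of the worst value during follow-up without saying that they depart from that rule, so the worst grade may be missed.

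**The case against.** The strongest reply is that this is a matter of presentation. The counting rules are correct. The listings show every event, examination and administered dose by subject, and with about 27 participants a careful reader can follow each case; a median onset in a group of three adds little. The once-per-SOC row narrows the count and sometimes fixes it. Protocol 7.3.2 asks for a diagnosis rather than signs, which limits splitting across terms. Grade 3 or 4 events have their own table (14.3.4). SAP section 1 allows supplementary analyses. Participant protection does not rest on these tables, because Protocol 10.7.5 has the Data and Safety Monitoring Committee (DSMC) see a summary of all available data. The remedy also comes late: the version 8.0 entry in Protocol Appendix C reports that a 12-month analysis had been done.

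Most of this stands. It shows that the point is a gap and not an error, and it keeps the size modest. It does not close the gap. Permission to add an analysis is not a plan for one, and no definition fixed in advance would govern a count made from the listings. The SOC row cannot separate inflammation from other events in its class. Table 14.3.4 leaves out lower grades. Follow-up runs to Year 5, so the final tables can still include the summary if its date is stated openly.

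**Conclusion.** The gap is real and worth closing. The number of participants with any intraocular inflammation may be known only within bounds, and onset, duration and recurrence appear in no planned table. Two stated rules add to this: summaries omit unscheduled visits, and the Group 4 and 3+4 columns may mix doses. The size cannot be given in advance, because it depends on coding and on MTDs that the documents do not give.

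Four stronger readings are tempting and are not supported:

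- *Inflammation in this trial prompted the steroids.* Protocol Appendix C says only that the DSMC recommended prophylaxis, and section 5.7 gives its purpose. The explicit link to events in this trial is for Group 2A.
- *Most of the 3+4 column is on mixed doses.* Groups 1A, 1B, 2 and 3 take 12 of about 27, leaving 15 for 2A and 4. Group 4 reaches 15 only if 2A is empty. Children are to be treated in 2A first, so Group 4 would then be all adult, with no adult and child mixing. A dose that the label does not print is not shown to be a mixed dose.
- *The macaque study shows what the human tables would reveal, or sets a threshold.* It describes recurrence and persistence in animals. The 2+ level mentioned there is not a human cut-off in either document.
- *The safety analysis is wrong.* It is correct as far as it goes.

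**What to change.** - Add intraocular inflammation (study eye, fellow eye) to the SAP 14.1 categories, defined by a dated PT list. State that open-label data and a 12-month analysis came before the list.
- Give one table by dose actually received, with each Group 4 participant placed by his own dose. Count each participant once in the grouped row and keep the single PT rows beneath it.
- Report n and %, maximum intensity, relationship to agent and to procedure, days from injection to first onset, number of episodes, and duration. Resolution and stabilization share one date field, so use the outcome field and mark ongoing or stabilized events separately.
- Include unscheduled visits in the worst-value slit-lamp and ophthalmoscopy shifts, and show the full 0 to 4+ grade distribution rather than a cut-off.

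The cost is one PT list, one extra table and a change to the shift tables, all from data already collected. Sample size, alpha and procedures do not change. The downside is that the headline percentage may look less favourable than any single PT row.

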14.2 Clinical Laboratory Data

14.2.1 Hematology and Clinical Chemistries

Hematology and clinical chemistry will be obtained at the screening or baseline visit and at 7 and 14 days after study agent administration. Hematology will include hemoglobin, hematocrit, white blood cell count with differential and platelet count. Clinical chemistry will include sodium, potassium, chloride, total protein, albumin, calcium, phosphorous, glucose, blood urea nitrogen, creatinine, total bilirubin, alkaline phosphatase, lactate dehydrogenase, aspartate aminotransferase and alanine aminotransferase.

The observed and change from baseline values of quantitative hematology and clinical chemistry parameters will be summarized by group at each visit with continuous descriptive statistics. Analyses will also include shifts from baseline to each post-baseline visit values using low, normal, and high classifications. Normal ranges will be used to determine the classifications. Values below the normal range will be classified as low, values above the normal range will be classified as high, and values within the normal range will be classified as normal.

Subject listings will be provided for hematology and clinical chemistries, separately, for each time point for all laboratory parameters and will include a column to distinguish abnormal values.

14.2.2 Coagulation

Coagulation tests (prothrombin time and partial thromboplastin time) will be obtained at the screening or baseline visit.

A subject listing will be provided for coagulation tests.

14.3 Immunology

Serum to measure antibodies to AAV will be obtained at the screening visit and at 1, 3, 6 and 12 months after study agent administration and at each long-term follow-up visit. Serum to measure antibodies to RS1 will be collected at the baseline visit and at 1, 3, and 12 months after study agent administration.

Peripheral blood mononuclear cells (PBMC) will be collected at the baseline visit and at 1, 2 and 3 months after study agent administration. Aliquots of these PBMC samples will be stored for possible future analyses including measurement of T cell responses to AAV or RS1.

Immune responses will be measured quantitatively (antibody titer, spot-forming cells per 10⁶ PBMC) and also as binary indicators of whether there is a measurable response to the target protein.

The observed and change from baseline values of quantitative immunology parameters will be summarized by group at each visit and time point (where appropriate) with continuous descriptive statistics. The qualitative results will be summarized with categorical descriptive statistics.

A subject listing will be provided for immunology parameters.

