### 4.2 Subject Exclusion Criteria

All subjects meeting any of the following exclusion criteria prior to enrollment will be excluded from study participation:

- 1. Prior receipt of any AAV gene therapy product,
- 2. Any of the following mutations in the RS1 gene: R141H, C59S or C223S,
- 3. Serum anti-AAV neutralizing antibody titer against AAV2tYF >1:20,
- 4. Pre-existing eye conditions that would contribute significantly to visual loss or increase the risk of an intravitreal injection (e.g. advanced glaucoma, uveitis or large retinal detachment),
- 5. Lens, cornea, or other media opacities that preclude adequate visualization and testing of the retina,
- 6. Use of anticoagulants or anti-platelet agents within 7 days prior to study agent administration,
- 7. Use of any investigational agent within 3 months prior to enrollment,
- 8. Any condition which leads the investigator to believe that the participant cannot comply with the protocol requirements or that may place the participant at an unacceptable risk for participation.

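### Antibody titers are summarised only on the raw scale, so in the groups of 3 the mean, SD and mean-change columns say little; add geometric mean titer and fold rise

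*SAP*

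**What the plan says.** SAP 14.3 (Immunology) names the quantitative measures: "Immune responses will be measured quantitatively (antibody titer, spot-forming cells per" a million PBMC). For these, "The observed and change from baseline values of quantitative immunology parameters will be summarized by group at each visit", using continuous descriptive statistics.

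SAP 9.4 (Data Analysis Conventions) fixes what that means: "Summaries for continuous and ordinal variables will include the number of observations (n), arithmetic mean, standard deviation (SD), median, minimum, and maximum". It also defines change: "Change from baseline will be calculated as follow-up visit values minus the baseline value". The result is presented as Table 14.4.4.

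The same SAP section treats immune response a second way, "and also as binary indicators of whether there is a measurable response to the target protein", and adds that "The qualitative results will be summarized with categorical descriptive statistics". Every value goes into Listing 16.2.9.

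Protocol 10.7 uses the same raw-scale mean and SD, plus quartiles. Protocol 10.7.4 adds the frequency of positive responses, by time point and cumulatively. Neither document mentions a geometric mean titer, a log transformation of titers, a fold rise, or the handling of a titer below the assay limit.

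On status, Protocol 2.2.1 and 7.1.2 list change in anti-RS1 titer as a safety outcome. SAP 3.3 lists it among other outcomes, and SAP 19 records the move.

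**The concern.** A titer is a dilution, as in the only titer the documents state, an eligibility limit for a different antibody: "Serum anti-AAV neutralizing antibody titer against AAV2tYF >1:20". On such a scale a doubling is one step wherever it starts. An arithmetic mean gives most of its weight to the highest value, the SD of raw titers then mainly reflects that value, and a difference from baseline mixes the size of the response with the starting level.

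Four of the reporting groups (1A, 1B, 2 and 3) have 3 participants and Group 2A has up to 6, so there is little to dilute one high value. Someone comparing dose groups on the mean column could rank them by the presence of one strong responder, not by how strongly participants generally responded. The Protocol's risk section says that the clinical consequences of an immune response to RS1 are not known, so the summary should be readable.

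**Working it through.** The plan gives no figure for titers, so there is none to reproduce. The statistics below are computed as SAP 9.4 defines them, on hypothetical titers.

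**Inputs.** Group sizes of 3 and 6 are from the design table (SAP 4.1). The baseline of 20 and all rises are assumptions; 20 merely borrows the anti-AAV eligibility limit.

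**Formulas.** Change = follow-up − baseline. Top share = largest change ÷ sum of changes. Geometric mean fold rise = (product of fold rises)^(1/n).

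**1. One high responder, the others rising 4-fold from 20 (20 to 80, change 60).** The high responder rises 64-fold (20 to 1280, change 1260).

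- n = 3: mean change (60 + 60 + 1260)/3 = 460, SD 693. Top share 1260/1380 = 91%. Without that participant the mean is 60. Geometric mean fold rise (4 × 4 × 64)^(1/3) = 10.1.
- n = 6: mean change (5 × 60 + 1260)/6 = 260, SD 490. Top share 1260/1560 = 81%. Geometric mean fold rise (4^5 × 64)^(1/6) = 6.35.

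Varying the top rise from 16- to 256-fold:

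| | n = 3 | n = 6 |
|---|---|---|
| Mean change | 140 to 1740 | 100 to 900 |
| Top share | 71% to 98% | 50% to 94% |
| Geometric mean fold rise | 6.35 to 16.0 | 5.04 to 8.0 |
| Median change | 60 throughout | 60 throughout |

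**2. Same response, different baselines.** Three participants each rise 16-fold, from 10, 20 and 160. The changes are 150, 300 and 2400, with mean 2850/3 = 950. One participant supplies 2400/2850 = 84% although all three responded equally. The geometric mean fold rise is 16.

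**3. Ranking two groups of 3.**

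- Group X: baseline 20 each, rises of 1-, 1- and 64-fold. Mean change 1260/3 = 420, SD 727. Geometric mean fold rise 64^(1/3) = 4.
- Group Y: baselines 10, 20 and 20, all rising 16-fold. Mean change (150 + 300 + 300)/3 = 250. Geometric mean fold rise 16.

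The raw mean puts X above Y; the fold rise puts Y above X. The planned median change (0 against 300) and minimum change (0 against 150) also put Y above X.

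**4. How usual is dominance?** Log-normal rises with a median of 16-fold and a spread of 1, 2 or 3 log2 units (assumed), 100,000 simulated groups each:

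| | Median top share, SD 1 / 2 / 3 | Top share above half, SD 1 / 2 / 3 | Equal share |
|---|---|---|---|
| n = 3 | 52% / 67% / 79% | 56% / 85% / 93% of groups | 33% |
| n = 6 | 33% / 49% / 62% | 7% / 48% / 71% of groups | 17% |

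So one participant usually supplies most of the mean change at n = 3. At n = 6 it depends on the spread.

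**The case against.** The strongest reply is that the planned output already shows a lone responder. The same row carries "arithmetic mean, standard deviation (SD), median, minimum, and maximum". With three evaluable participants, the minimum, median and maximum are the three values. For titers of 20, 20 and 2560 the arithmetic mean is 2600/3 = 867, but the row also shows median 20, minimum 20 and maximum 2560. A rise in everyone cannot be hidden either: the minimum change is above zero exactly when every evaluable participant rose. The responder summary and the listing show the rest. This stands. A reader might infer that one participant determines the reported immune response, or that the table could pass off one responder as a group response. The documents do not support that.

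Some limits remain. With two evaluable participants the median equals the mean, though minimum and maximum still show both values. The binary indicator records a measurable response, not its size. Protocol 1.3.1 expects most participants to develop antibodies to AAV, so for that antibody the indicator may separate groups poorly. The Protocol's quartiles and cumulative prevalence are not repeated in the SAP, whose methods supersede the Protocol's.

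A second reply is that a geometric mean can mislead too. If those three participants all began at 20, the fold rises are 1, 1 and 128; the geometric mean titer is 101 and the geometric mean fold rise 128^(1/3) = 5.04, though two did not respond. This also stands. The log-scale columns complement the median, range and responder count and cannot replace them.

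A third reply is that the documents give no RS1 titer range, dilution scheme or assay limit. That is so, and it makes every magnitude above illustrative. Nor do the documents say that below-limit results will count as missing. SAP 9.2 leaves missing data unimputed, and the plan is silent on whether a below-limit result has a value.

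**Conclusion.** The point holds in a limited form. For antibody titers the mean, SD and mean-change columns are on the wrong scale and are largely uninformative in the groups of 3 and, with wide spread, in a group of 6. They also weight equal fold rises by baseline. In the illustrations one participant supplies 71% to 98% of the summed change at n = 3 and 50% to 94% at n = 6. These figures assume dilution titers, a baseline of 20 and 4-fold rises in the others.

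The consequence is small. Other columns of the same table, the responder summary and the listing give the right reading. Immunology has no hypothesis test, the definition of dose-limiting toxicity uses no titer threshold, and the SAP ranks the anti-RS1 titer as an other outcome, although the Protocol lists it under safety. A reader might infer from the Protocol's listing that the safety conclusion is at risk; nothing in the documents ties that conclusion to the mean titer. Severity is low.

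**What to change.** In SAP 14.3 and Table 14.4.4, for antibody titers:

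- replace or supplement the arithmetic mean, SD and change with geometric mean titer, geometric SD and geometric mean fold rise from baseline;
- assign titers below the assay limit a stated constant, so that they enter the summaries and are not treated as missing;
- keep the median, minimum, maximum, responder proportion and subject listing.

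This changes a table shell and its programming and needs no new data or visits: a free improvement. The version 8.0 entry in the Protocol's change summary records that a 12-month analysis has been done. If that table already exists, the log-scale version can be added as a supplementary analysis identified in the study report, which the SAP introduction allows.
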